## 5.0 SELECTION OF STUDY POPULATION

### 5.1 Inclusion Criteria

An eligible patient must meet all of the following criteria:

1. Provide written, informed consent to participate in the study and follow the study procedures. The Investigator takes responsibility for ensuring that all vulnerable patients are protected and participate voluntarily in an environment free from coercion or undue influence. The patient may also provide consent for additional research (described in Section 8.3.3). However, the patient may participate in the study without participating in additional research.
2. Male or female patients, age 18 years or older at the time of signing the informed consent form (ICF).
3. Have histologically or cytologically-confirmed recurrent or metastatic HNSCC that is considered incurable by local therapies.
  - a. No prior systemic therapy for recurrent or metastatic disease. Systemic therapy given as part of multimodal treatment for locally advanced disease is allowed if completed more than 6 months prior to signing consent.
  - b. The eligible primary tumor locations are oropharynx, oral cavity, hypopharynx, and larynx.
  - c. Patients may not have a primary tumor site of nasopharynx (any histology) and/or unknown primary.
4. Have measurable disease based on RECIST 1.1 as determined by the local site Investigator. Tumor lesions situated in a previously irradiated area are considered measurable if progression has been shown in such lesions since irradiation.
5. Eastern Cooperative Oncology Group (ECOG) performance status of 0 or 1 (see Appendix 3).
6. Provide tumor tissue from a core, incisional, or excisional biopsy (fine needle aspirates are not acceptable) to the central laboratory for determination of PD-L1 status (if not determined at local laboratory) [REDACTED]. Repeat samples may be required if adequate tissue is not provided for assessment of PD-L1 status. A newly obtained biopsy is strongly preferred, but archival tumor biopsy may be used and provided (see Section 8.3.1).
7. The tumor must have positive PD-L1 expression (ie, CPS  $\geq$  1) as determined by a local or the central laboratory with the IHC 22C3 PharmDx diagnostic kit.

8. Patients with oropharyngeal cancer: must have results from testing of HPV status defined as p16 IHC testing using CINtec® p16 Histology assay. If HPV status was previously tested using this method, no additional testing is required. Note:
- Tumor p16 expression must be evaluated by assessment of IHC analysis with CINtec® p16 Histology assay (Ventana Medical Systems Inc., Tucson AZ) using ‘Benchmark Ultra’ autostainer (Ventana, Tucson, AZ) and standard protocol. Positive p16 expression is defined as strong and diffuse nuclear and cytoplasmic staining in 70% or more of the tumor cells.
  - If local p16 testing results are not available, or cannot be assessed by the specified method, a tumor tissue sample may be submitted to the central laboratory for p16 testing.

Patients with oral cavity, hypopharynx, or larynx cancers: HPV testing by p16 IHC is not required as by convention these tumor locations are assumed to be HPV negative.

9. Demonstrated adequate organ function as defined below (see Section 10.18 for clinical laboratory test information):

System	Laboratory Value
Hematological	
Absolute neutrophil count (ANC)	$\geq 1500/\mu\text{L}$ ( $1.5 \times 10^9/\text{L}$ ) without myeloid growth factor support for 7 days preceding the lab assessment
Platelets	Platelet count $\geq 100,000/\mu\text{L}$ ( $100 \times 10^9/\text{L}$ ) without platelet transfusions for 7 days preceding the lab assessment
Hemoglobin	Hemoglobin $\geq 9.0$ g/dL (90 g/L) without erythropoietin-stimulating agents or transfusion for 14 days preceding the lab assessment
Renal	
Serum creatinine OR measured or calculated creatinine clearance a (GFR can also be used in place of creatinine or creatinine clearance)	$\leq 1.5 \times \text{ULN}$ OR $\geq 60$ mL/min for patients with creatinine levels $> 1.5 \times \text{ULN}$
Hepatic	
Total bilirubin	$\leq 1.5 \times \text{ULN}$ OR Direct bilirubin $\leq \text{ULN}$ for patients with total bilirubin $> 1.5 \times \text{ULN}$
AST or ALT	$\leq 2.5 \times \text{ULN}$
Digestive	
Lipase and amylase	$\leq 1.5 \times \text{ULN}$ Patients with pancreatic metastases and lipase and/or amylase $< 3 \times \text{ULN}$ may enroll. Patients may not enroll if there are clinical or radiographic signs of pancreatitis.
Coagulation	
INR or PT aPTT	$\leq 1.5 \times \text{ULN}$ unless the patient is receiving anticoagulant therapy, as long as PT or aPTT is within the therapeutic range of intended use of anticoagulants

Abbreviations: ALT (SGPT) = alanine transaminase (serum glutamic pyruvic transaminase); aPTT = activated partial thromboplastin time; AST (SGOT) = aspartate transaminase (serum glutamic oxaloacetic transaminase); GFR = glomerular filtration rate; INR = international normalized ratio; PT = prothrombin time; ULN = upper limit of normal

- Creatinine clearance should be calculated according to institutional standard.

10. A documented left ventricular ejection fraction (LVEF)  $> 45\%$  using standard echocardiogram or multigated acquisition (MUGA) scan test.
11. Patients with hypertension must be on a stable antihypertensive regimen for the 14 days prior to the first dose of study drug. Need for  $\leq 2$  antihypertensive medications for management of hypertension (including diuretics) permitted (for patients randomized to Arm A receiving bempegaldesleukin: Section 6.7.2.2 provides additional on-treatment considerations regarding antihypertensive medications).
12. Oxygen saturation  $\geq 90\%$  on room air.
13. Clinically significant toxic effect(s) of the most recent prior anticancer therapy must be Grade 1 or resolved (except alopecia, neuropathy, adrenal insufficiency and hypothyroidism). Note:
  - a. Patients with  $\leq$  Grade 2 neuropathy are eligible.
  - b. Patients with endocrine-related AEs Grade  $\leq 2$  requiring treatment or hormone replacement may be eligible. Specifically, patients with Grade  $\leq 2$  adrenal insufficiency (defined as requiring medical intervention, such as concomitant steroids) or Grade  $\leq 2$  hypothyroidism (defined as requiring hormone replacement therapy) may be enrolled provided that clinical symptoms are adequately controlled and the daily dose is 10 mg or less of prednisone or equivalent.
  - c. If the patient had a major operation, the patient must have recovered adequately from the procedure and/or any complications from the operation before starting study intervention.
14. Reproductive Status
  - a. Women of childbearing potential (WOCBP) must have a negative highly sensitive pregnancy test (urine or serum as required by local regulations) within 24 hours for urine or within 72 hours for serum before the first dose of study treatment.  
Note: If a urine test cannot be confirmed as negative (eg, an ambiguous result), a serum pregnancy test is required. In such cases, the patient must be excluded from participation if the serum pregnancy result is positive.
  - b. Women must not be breastfeeding.
  - c. WOCBP must agree to follow instructions for method(s) of contraception for the duration of treatment with study treatment and for at least 120 days after the last dose of study treatment or 30 days after cessation of study drug if the patient initiates a new anticancer treatment. Women should use an adequate method(s) of contraception as indicated in [Appendix 5](#). WOCBP who are continuously not heterosexually active are exempt from contraceptive requirements, and still must undergo pregnancy testing as described in this protocol.

Note: The Investigator is responsible for review of medical history, menstrual history, and recent sexual activity to decrease the risk for inclusion of a woman with an early undetected pregnancy.

- d. For Arm A: Males who are sexually active with WOCBP must agree to follow instructions for method(s) of contraception for the duration of treatment with study treatment(s) and at least 3 months after the last dose of bempegaldesleukin. In addition, male patients must be willing to refrain from sperm donation during this time ([Appendix 5](#)).

For Arm B: For males receiving pembrolizumab monotherapy, there are no contraception requirements.

15. Patients who are hepatitis B surface antigen (HBsAg) positive are eligible if they have received hepatitis B virus (HBV) antiviral therapy for at least 4 weeks and have undetectable HBV viral load prior to randomization.  
Note: Patients should remain on antiviral therapy throughout study intervention and follow local guidelines for HBV antiviral therapy post completion of study intervention. Hepatitis B screening tests are not required unless:
- Known history of HBV infection
  - As mandated by local health authority
16. Patients with history of hepatitis C virus (HCV) infection are eligible if HCV viral load is undetectable at screening.  
Note: Patients must have completed curative antiviral therapy at least 4 weeks prior to randomization. Hepatitis C screening tests are not required unless:
- Known history of HCV infection
  - As mandated by local health authority
17. Patients must be able and willing to comply with the study visit schedule and study procedures.

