### 6.5.2.1.2 Immune-related AEs Associated with Pembrolizumab

AEs associated with pembrolizumab exposure may represent an immune-related response. These irAEs may occur shortly after the first dose or several months after the last dose of pembrolizumab treatment and may affect more than one body system simultaneously. Therefore, early recognition and initiation of treatment is critical to reduce complications. Based on existing clinical study data, most irAEs were reversible and could be managed with interruptions of pembrolizumab, administration of corticosteroids and/or other supportive care. For suspected irAEs, ensure adequate evaluation to confirm etiology or exclude other causes. Additional procedures or tests such as bronchoscopy, endoscopy, skin biopsy may be included as part of the evaluation.

Dose modification and toxicity management guidelines for irAEs associated with pembrolizumab are provided in [Table 6](#). These guidelines apply to patients **receiving bempegaldesleukin in combination with pembrolizumab OR either treatment as a monotherapy**.

For toxicities requiring treatment discontinuation, bempegaldesleukin or pembrolizumab alone may continue as a monotherapy if the toxicity is considered not related to that study drug by the Investigator.

**For patients in Arm A receiving bempegaldesleukin**, elevations of AST or ALT occurring in Cycle 1 should be managed according to the guidelines in Section [6.5.1.1.2](#). For elevations of AST or ALT occurring in Cycle 2 or beyond, follow the dose modification and toxicity management guidelines in [Table 6](#).

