## 10.16 Pregnancy Tests/Pregnancy

### 10.16.1 Pregnancy Tests

Serum or urine pregnancy tests will be performed on women of childbearing potential (WOCBP) according to the Schedule of Events (Section 1.2). Pregnancy testing (urine or serum as required by local regulations) should also be conducted 120 days after the last dose of study drug.

Pregnancy testing requirements for study inclusion are described in Section 5.1.

Pregnancy testing (urine or serum as required by local regulations) should be conducted prior to every cycle (q3w) or more frequently if required by local regulations.

Additional serum or urine pregnancy tests may be performed, as determined necessary by the investigator or required by local regulation, to establish the absence of pregnancy at any time during the subject's participation in the study.

Urine pregnancy tests should have a highly sensitive pregnancy test. A negative pregnancy test result must be obtained before the administration of the study drug(s).

A pregnancy test does not need to be performed on women who are postmenopausal (see Appendix 5) for at least 1 year or surgically sterile for at least 3 months before signing the ICF.

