### 10.16.2 Pregnancy

#### 10.16.2.1 Pregnancy and Lactation in Female Patients

The Sponsor must be notified immediately without undue delay, under no circumstances later than 24 hours following knowledge of the initial report and any follow-up reports of a female patient becoming pregnant or breastfeeding during the course of the study and for 120 days after the last dose of study drug or 30 days after cessation of study drug if the patient initiates a new anticancer treatment for female patients. All reports should be submitted via the Pregnancy Notification Form. Pregnancy, although reportable, is not considered an AE/SAE unless a female patient experiences signs or symptoms of pregnancy complications; however, the contact information for pregnancy reporting is the same as for SAE reporting and listed in Section 10.7. Female patient(s) who become pregnant will be followed until the outcome of the pregnancy is known. Pregnancy follow-up should describe the outcome of the pregnancy, including any voluntary or spontaneous termination, details of the birth, and the presence or absence of any congenital abnormalities or birth defects in the offspring. Pregnancy outcomes of ectopic pregnancy, spontaneous abortion, missed abortion, benign hydatidiform mole, blighted ovum, fetal death, intrauterine death, miscarriage, and stillbirth must be reported as serious events (Important Medical Events). If the pregnancy continues to term, the outcome (health of infant) must also be reported.

If a female patient becomes pregnant, administration of the study drug(s) must be discontinued immediately.

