### 10.16.2.2 Arm A Only: Pregnancies in Female Partners of Male Patients

For patients treated with bempegaldesleukin, any pregnancy occurring during the course of the study and for 3 months after the last dose of bempegaldesleukin in a female partner of a male patient must be reported to the Sponsor. The Sponsor must be notified immediately without undue delay, under no circumstances later than 24 hours following knowledge of the initial report and any follow-up information. All reports should be submitted via the Pregnancy Notification Form. In order for the Sponsor or designee to collect any pregnancy surveillance information, the pregnant patient or partner must sign an informed consent form (See Section 14.2).

Pregnancy, although reportable, is not considered an AE/SAE unless a female partner of a male patient experiences signs or symptoms of pregnancy complications; however, the contact information for pregnancy reporting is the same as for SAE reporting and listed in Section 10.7. Attempts should be made to collect and report details of the course and outcome of any pregnancy in the partner of a male patient exposed to study drug with the authorization from the pregnant partner. Pregnancy follow-up should describe the outcome of the pregnancy, including any voluntary or spontaneous termination, details of the birth, and the presence or absence of any congenital abnormalities or birth defects in the offspring. Pregnancy outcomes of ectopic pregnancy, spontaneous abortion, missed abortion, benign hydatidiform mole, blighted ovum, fetal death, intrauterine death, miscarriage, and stillbirth must be reported as serious events (Important Medical Events). If the pregnancy continues to term, the outcome (health of infant) must also be reported.

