### 14.2 Written Informed Consent

Written documentation of informed consent must be obtained from each patient or (if permitted by the local health authority) a patient's legal representative before entering the study. Patients will be informed of the nature of the study, and the ICF must be presented to each patient in the language in which the patient is fluent.

Informed consent will be obtained from and documented for each patient prior to the conduct of any protocol-specific procedures. Signed and dated ICFs will be retained by the Investigator with the study records. Each patient will be given a copy of the signed and dated ICF.

Any pregnancy that occurs in a study patient or the female partner of a male study patient should be reported to the Sponsor or designee. For the Sponsor or designee to collect any pregnancy surveillance information, the pregnant patient or partner must sign an informed consent form for disclosure information. Information on this pregnancy will be collected on the Pregnancy Surveillance Form.

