**CONTRACEPTION GUIDANCE FOR FEMALE PATIENTS OF CHILDBEARING POTENTIAL**

One of the highly effective methods of contraception listed below is required during study duration and until the end of relevant systemic exposure, defined as 120 days after the last dose of study treatment (Note: local laws and regulations may require use of alternative and/or additional contraception methods).

Highly Effective Contraceptive Methods That Are User Dependent  Failure rate of < 1% per year when used consistently and correctly.a

Combined (estrogen- and progestogen-containing) hormonal contraception associated with inhibition of ovulationb
 
 
• oral
 
• intravaginal
 
• transdermal
 

Progestogen-only hormonal contraception associated with inhibition of ovulationb
 
 
• oral
 
• injectable
 

Highly Effective Methods That Are User Independent

 
• Implantable progestogen-only hormonal contraception associated with inhibition of ovulationb
 
• Hormonal methods of contraception including vaginal ring, injectables, implants and intrauterine hormone-releasing system (IUS)c
 
• Intrauterine device (IUD)c
 
• Bilateral tubal occlusion
 

 
• Vasectomized partner  A vasectomized partner is a highly effective contraception method provided that the partner is the sole male sexual partner of the WOCBP and the absence of sperm has been confirmed. If not, an additional highly effective method of contraception should be used.
 

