## CONTRACEPTION GUIDANCE FOR MALE PATIENTS WITH PARTNER(S) OF CHILDBEARING POTENTIAL

For Arm A (bempegaldesleukin plus pembrolizumab): male patients with female partners of childbearing potential are eligible to participate if they agree to the following during the treatment and until the end of relevant systemic exposure.

- Inform any and all partner(s) of their participation in a clinical drug study and the need to comply with contraception instructions as directed by the Investigator.
- Male patients are required to use a condom for study duration and until end of relevant systemic exposure defined as 3 months after the last dose of bempegaldesleukin.
- Female partners of males participating in the study to consider use of effective methods of contraception until the end of relevant systemic exposure, defined as 3 months after the last dose of bempegaldesleukin in the male patient.
- Male patients with a pregnant or breastfeeding partner must agree to remain abstinent from penile vaginal intercourse or use a male condom during each episode of penile penetration during the treatment and until 3 months after the last dose of bempegaldesleukin.
- Refrain from donating sperm for the duration of the study treatment and until 3 months after the last dose of bempegaldesleukin.

For Arm B (pembrolizumab monotherapy): For male patients receiving pembrolizumab monotherapy, there are no contraception requirements.

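### For a woman who starts a new anticancer treatment, inclusion criterion 14c lets contraception end as early as day 30, while Appendix 5 requires it to day 120 without exception

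*Protocol*

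**What the plan says.** Criterion 14c sets a default of at least 120 days of contraception and then a shorter alternative: "after the last dose of study treatment or 30 days after cessation of study drug if the patient initiates a new anticancer treatment". For the methods to use, it sends the reader to Appendix 5.

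Appendix 5, in its guidance for female patients, requires one of the listed highly effective methods during the study and "until the end of relevant systemic exposure, defined as 120 days after the last dose of study treatment". The only qualifier there is that local law may call for alternative or additional methods. Nothing shortens the period.

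Section 10.16.1 says that a pregnancy test "should also be conducted 120 days after the last dose of study drug", again without a new-treatment exception. Table 1 also marks a pregnancy test at Follow-Up Visit 2 (day 90 ± 7), and Section 6.3.1 holds that visit whether or not new therapy has begun.

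Section 10.16.2.1 requires the sponsor to be told within 24 hours of a pregnancy or breastfeeding in a female patient while the study runs and up to day 120, with the same shorter alternative. The window is counted from "the last dose of study drug or 30 days after cessation of study drug if the patient initiates a new anticancer treatment".

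**The concern.** Appendix 5 ties the duration to exposure to study drug. Starting a different treatment does not remove drug already given, so it cannot bring forward the end of the exposure period that the protocol has defined. The protocol gives no reason for the shorter limit.

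Criterion 14c is the undertaking that a woman gives at entry, so it is the text a site is likely to apply when counselling her. If it is applied as written, she may stop contraception and conceive while still inside the protocol's own exposure window. What is at stake is participant protection. No efficacy endpoint, error rate or sample size is affected.

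**Working it through.** No statistical figure is involved. The check sets the rules side by side and measures the gap.

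**Inputs for a woman who starts new anticancer treatment**

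| Source (Protocol) | Rule | End point |
|---|---|---|
| Section 5.1, 14c, default | contraception | day 120 |
| Section 5.1, 14c, new treatment | contraception | day 30 after cessation |
| Appendix 5, female patients | contraception | day 120, no exception |
| Table 1 and Section 6.3.1 | pregnancy test | day 90 ± 7, regardless of new therapy |
| Section 10.16.1 | pregnancy test | day 120, no exception |

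**Gap in contraception.** Let t be the day after the last dose on which new treatment starts, and take last dose and cessation as the same day. Until t, the 120-day default in 14c applies. From t, the 30-day limit applies, so the duty under 14c ends at max(30, t). Appendix 5 ends at 120. For t up to 120:

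gap = 120 − max(30, t)

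- t ≤ 30: 120 − 30 = 90 days
- t = 60: 120 − 60 = 60 days
- t = 90: 120 − 90 = 30 days
- t = 120: 0 days

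The documents do not say when new treatment is expected to start, so the range is 0 to 90 days. The maximum needs new treatment by day 30.

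**Can both texts be satisfied?** Yes. The 120 days in Appendix 5 also meet 14c. The reverse fails: stopping at day 30 meets 14c and breaches Appendix 5.

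**Notification.** Three other provisions bear on a pregnancy found after day 30:

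- Section 6.6 requires the investigator to notify the sponsor within 24 hours of learning of a pregnancy in a female patient, and states no time window. The same sentence stops study drug, so it can be read as an on-treatment rule, but it is not limited to that.
- The Pregnancy row of Table 11 asks for all cases through the follow-up period, within 24 hours. Footnote a includes Follow-Up Visit 2 in that period, although it describes that visit as reporting SAEs only.
- Section 10.16.2.1 itself covers the course of the study as well as the post-dose window. Patients remain in survival follow-up (Section 6.3.2), and the study may run up to 5 years after the last patient's first dose (Section 6.4).

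A positive test at day 90 is therefore covered by a 24-hour rule on at least one natural reading. A positive test at day 120 is more arguable, but is still caught by Section 6.6 or by the broad reading of Section 10.16.2.1.

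**The case against.** The strongest reply is that this is a wording mismatch of little consequence. A careful site will apply the longer period and satisfy both texts. The 90 days is a maximum. The number of women affected is not given and must be smaller than the number of women of childbearing potential. The SAP records that the trial was discontinued with one patient enrolled and treated. Section 10.7 uses a similar 30-day cut for SAE reporting once new therapy starts, so the clause may be a deliberate sponsor convention. All of this limits the impact. It does not make the two contraception rules agree, and a limit suited to attributing adverse events is not a reason to shorten a period defined by exposure.

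Three stronger readings are tempting, and the documents do not support them.

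- *Pregnancy reporting lapses at day 30, or contradicts Section 14.2.* Section 14.2 does say "Any pregnancy that occurs in a study patient or the female partner of a male study patient should be reported to the Sponsor", with no window. It is a general sentence introducing the consent needed to collect pregnancy information, and it can stand beside specific rules that carry a deadline. Section 6.6, Table 11 and the reference to the course of the study in Section 10.16.2.1 already supply a 24-hour duty for most cases.
- *Late immune effects show fetal risk after day 30.* Section 6.5.2.1.2 says that immune-related events "may occur shortly after the first dose or several months after the last dose of pembrolizumab treatment". That concerns adverse events in the patient and says nothing about a pregnancy.
- *Men are held to a stricter standard.* Contraception for Arm A men runs "until end of relevant systemic exposure defined as 3 months after the last dose of bempegaldesleukin", and partner reporting covers "any pregnancy occurring during the course of the study and for 3 months after the last dose of bempegaldesleukin", both without a new-treatment cut. These rules concern bempegaldesleukin only, and Arm B men have no requirement, so periods that differ by sex and drug are to be expected. The comparison is weak support at best.

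**Conclusion.** The contraception conflict stands on the text of 14c and Appendix 5 alone. For a woman of childbearing potential who starts new anticancer treatment, the entry criterion allows contraception to stop up to 90 days before the end of what Appendix 5 defines as relevant systemic exposure. The size rests on two assumptions: that last dose and cessation of study drug fall on the same day, and that new treatment starts by day 30. A later start shrinks the gap day for day.

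The 30-day cut in Section 10.16.2.1 is out of line with the day-120 test in Section 10.16.1. That is a lesser inconsistency, and it does not show that the duty to report has been lost.

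Overall this is a participant-protection inconsistency that is cheap to correct. It has no bearing on the validity of the trial's comparisons.

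**What to change.** 1. In Section 5.1, criterion 14c, delete the alternative that ends contraception 30 days after cessation when new anticancer treatment starts, so that it runs to day 120 in every case, as in Appendix 5.
2. For harmonisation, delete the same alternative from Section 10.16.2.1, so that the notification window matches the day-120 test.
3. Optionally, state the 120-day window in the Pregnancy row of Table 11 and show the day-120 test in Tables 1 and 2.

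If the sponsor wants to keep the exception, it should justify it against the exposure definition and write it into Appendix 5 and Section 10.16.1 as well.

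The cost is up to 90 more days of contraception for the few women concerned, which Appendix 5 already requires, and clear 24-hour notification over the same period. No test is added, because Section 10.16.1 already asks for one at day 120. Table 1 has no day-120 visit, so sites need a visit or a local test for it either way. The 30-day cut for SAEs in Section 10.7 would remain. Since Section 10.16.2.1 treats outcomes such as miscarriage and stillbirth as serious events, a cross-reference there would help.
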